11. PHARMACOKINETIC ANALYSIS

Serum concentration of TEV-48574 will be listed, and summary statistics will be presented by visit. Pop-PK and PK/PD analysis will be conducted per separate analysis plans and reported separately (see Section [2.4.3](#)).

Serum concentrations that are below the limit of quantification (BLQ) will be treated as 0 for calculation of concentration descriptive statistics.

PK collections that have an actual sampling time that deviates from predefined collection time window (+/- 3days) or that are collected post-dose will be flagged in the data listing and excluded from the calculation of serum concentration summary statistics.

Summary statistics for serum concentration of TEV-48574 will include n, arithmetic mean, SD, arithmetic CV%, median, minimum, and maximum. The summaries will be presented by indication and treatment group, by visit. Serum concentrations will be reported to 3 significant digits in summary statistics except CV%, which will be reported to 1 decimal place.

The PK analysis set will be used for the PK analyses.

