
An exploratory objective of this trial is to evaluate association among exploratory biomarkers and clinical efficacy of TEV-48574 in adult participants with IBD (moderate to severe UC or CD).
	
 • Change from baseline at weeks 2, 4, 8, and 14 in protocol specified- serum-resident pharmacodynamic (PD) markers • Change from baseline in serum and/or gastrointestinal (GI) tissue markers of GI tissue condition (at weeks 2, 4, 8, and 14 for serum; at week 14 for tissue) • Change from baseline at week 14 in GI tissue transcriptome • Change from baseline in fecal calprotectin at weeks 2, 4, 8, and 14 • Change from baseline in high sensitivity C-reactive protein (hsCRP) at weeks 2, 4, 8, and 14 • Change from baseline in blood albumin levels at weeks 2, 4, 8, and 14 • Change from baseline in serum free and total tumor necrosis factor (ligand) 1A at weeks 2, 4, 8, and 14 • Change from baseline at week 14 in GI tissue tumor necrosis factor (ligand) 1A (TL1A) expression • Change from baseline in UC-100 at week 14 in participants with moderate to severe UC • Change from baseline in [REDACTED] at week 2, 8, and 14

Objectives	Endpoints

An exploratory objective of the trial is to obtain trough serum TEV-48574 concentrations, to compare major pharmacokinetic (PK) characteristics between UC and CD participants with healthy volunteers and asthma participants, and, if data allows, to evaluate the pharmacokinetics/pharmacodynamics and/or exposure-response relationship of 3 different dose regimens of TEV-48574 sc.
	
 • Trough serum TEV-48574 concentrations throughout the trial (sparse sampling) • Population pharmacokinetic parameters (e.g., clearance, volume of the central compartment, area under the concentration-time curve, maximum observed drug concentration, and trough drug concentration) • Population pharmacokinetic-pharmacodynamic parameters • Exposure-response parameters

An exploratory objective of this trial is to evaluate the effect of genetic polymorphisms on clinical efficacy in adult participants with IBD (moderate to severe UC or CD).
	
 1. Primary and other efficacy endpoints

In addition, the following efficacy endpoints are considered as exploratory endpoints:

- PRO2-UC items at weeks 2, 4, 6, 8, 10, 12 and 14
- PRO2-UC total score at weeks 2, 4, 6, 8, 10, 12 and 14
- CDAI score at weeks 4, 8, 12 and 14
- CDAI remission at weeks 4, 8, and 12

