Treatment and Follow-Up Period: During the 14-week treatment period, participants will visit the site Q2W on days 1, 15, 29, 43, 57, 71, and 85 (± 3 days) for investigational medicinal product (IMP) administration (7 visits), as well as an end-of-treatment visit on day 99 (± 3 days; week 14). After the end of the 14-week treatment period, all participants may be offered the option to enter a long-term extension trial described in a separate protocol (TV48574-IMM-20038). If they enter the long-term extension trial, they will not need to complete the follow-up visit in this trial. All other participants will return to the site for a follow-up visit (day 127 [± 3 days]). For those participants who enter the long-term extension trial, adverse events and concomitant medication data will be recorded in the dose-ranging trial case report form (CRF) up until the date of extension trial randomization (defined as the trial completion date for the dose-ranging trial). For those participants who screen fail the long-term extension trial, adverse events and concomitant medication data will be recorded in the dose-ranging trial up until the follow-up visit (day 127 [± 3 days]) CRF. Participants who complete the last scheduled visit will be considered to have completed the trial.

Participants who withdraw from the trial before completing the 14-week- treatment period will complete the assessments for the early termination visit and will be encouraged to complete the follow-up period in the trial.

The end of the trial is defined as the last visit of the last participant.

The total duration of participation in the trial is planned to be up to 24 weeks for each individual participant.

Trial procedures and assessments with respective time points are shown in Table 4 of the Trial Protocol.

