3. ANALYSIS SETS

3.1. Intent-to-Treat Analysis Set

The intent-to-treat (ITT) analysis set for each indication (UC or CD) will include all randomized participants.

In the ITT analysis set, participants will be categorized by treatment to which participants were randomized, regardless of which treatment they actually received.

Data collected from participants after treatment discontinuation will be included in the ITT analysis set.

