3.5. Pharmacokinetic Analysis Set

The pharmacokinetic (PK) analysis set will include all participants in the safety set who receive TEV-48574 and who have at least 1 reportable serum concentration result.

Participants with kit mix-ups will be excluded from the PK analysis set.

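### Section 11 screens serum concentrations by sampling window and post-dose draw but not by whether the preceding dose was given, so non-trough samples can enter the by-visit trough summaries

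*SAP*

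**What the plan says.** - **Sample-level rule (SAP Section 11).** "PK collections that have an actual sampling time that deviates from predefined collection time window (+/- 3days) or that are collected post-dose will be flagged". Such samples stay listed but are "excluded from the calculation of serum concentration summary statistics". No other sample-level ground is given. The summaries are by indication, treatment group and visit, and include arithmetic mean, SD, CV and median.
- **Participant-level rule (SAP Section 3.5).** The PK set takes safety-set participants "who receive TEV-48574 and who have at least 1 reportable serum concentration result". The one exclusion is: "Participants with kit mix-ups will be excluded from the PK analysis set". There is no condition on doses received.
- **What is being measured (SAP Section 1.3).** The exploratory endpoint is "Trough serum TEV-48574 concentrations throughout the trial (sparse sampling".
- **Visit windows (SAP Section 2.1).** "participants will visit the site Q2W on days 1, 15, 29, 43, 57, 71, and 85 (± 3 days) for investigational medicinal product (IMP) administration". The end-of-treatment visit on day 99 and the follow-up visit on day 127 carry the same tolerance. These are calendar windows. Section 11 does not say whether its own window is one of them.
- **Off-schedule dosing is foreseen.** Section 8.3 tabulates adverse events leading to dose interruption, and Section 8.2 tabulates the number of doses received. Section 1.2 lists treatment discontinuation separately from early termination. Section 3.1 says: "Data collected from participants after treatment discontinuation will be included in the ITT analysis set". That last sentence defines the ITT set, not the PK set.
- **Loading dose only (SAP Section 3.3).** A participant who received the loading dose and no induction dose is placed in the 450 mg arm of the safety set, from which the PK set is drawn.

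**The concern.** A pre-dose sample at a Q2W visit is a trough for that regimen only if the previous dose was given about 14 days earlier. The two filters in Section 11 show that the tables are meant to hold troughs, and the kit mix-up exclusion shows that they are meant to reflect the assigned regimen. Neither filter looks at the preceding dose. A sample taken after a missed dose can therefore be averaged with true troughs. So can a sample taken after treatment discontinuation, if PK is still drawn then.

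At stake is the reading of the by-visit concentration tables. Means would be pulled down and spread widened by missed dosing, and the table alone would not show why. Section 2.4.3 puts population PK and exposure-response work outside this SAP and allows that it may not appear in the CSR. These tables may therefore be the main PK result that a CSR reader sees.

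**Working it through.** The SAP gives no figure on this point, so there is nothing to reproduce. The check has a timing part, which rests on the text, and an illustration, which rests on assumptions.

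**1. Does a missed-dose sample pass the filters?** Take the day 99 (±3) visit, with doses on their nominal days.
- Day 85 dose given: 96 − 85 = 11 to 102 − 85 = 17 days since the last dose.
- Day 85 dose missed, last dose on day 71: 96 − 71 = 25 to 102 − 71 = 31 days.

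The second sample is inside the calendar window and is not post-dose, so Section 11 keeps it. If the window instead ran from the previous dose (14 ± 3 days, or 11 to 17), the same sample would fall outside and be dropped. The result turns on the anchor, which the SAP does not state.

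**2. How far could the mean move?** Assumptions, none from the SAP: mono-exponential decline, similar on-schedule troughs at adjacent visits, half-life h of 7, 14 or 21 days, and a share f of 5, 10 or 15% of sampled participants one dose behind.

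Ratio to an on-schedule trough after one missed dose: r = 2^(−14/h). Change in the visit mean: −f(1 − r).

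| h (days) | r | f = 5% | f = 10% | f = 15% |
|---|---|---|---|---|
| 7 | 0.25 | −3.75% | −7.5% | −11.25% |
| 14 | 0.50 | −2.5% | −5.0% | −7.5% |
| 21 | 0.63 | −1.85% | −3.7% | −5.55% |

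The range is about 2 to 11%.

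**3. Loading dose only, counted at 450 mg.** Under the same decline, compare what remains 98 days after the loading dose with full dosing:
- L = 2250 × 2^(−98/h)
- full = L + the sum over j = 1 to 6 of 450 × 2^(−(98 − 14j)/h)

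For h = 14, L = 2250/128 = 17.6 and full = 17.6 + 443.0 = 460.5, so L/full = 0.038. For h = 7 and h = 21 the ratio is 0.001 and 0.110. Such a participant would contribute about 0.1 to 11% of an on-schedule 450 mg trough, provided a week 14 sample is drawn at all.

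**The case against.** The strongest reply is that the anchor is inferred. Section 11 calls the window predefined without defining it, and the schedule of assessments is in the protocol, which is not at hand. If the window runs from the previous dose, samples after a missed dose are already excluded. This stands, and the conclusion is conditional for that reason. The calendar reading is the natural one because the only other ±3 day windows in the SAP are visit windows.

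Second, sampling after discontinuation is not established. Section 3.1 concerns the ITT set, and Section 2.1 sends participants who withdraw from the trial to an early termination visit. This also stands. The missed-dose case does not depend on it.

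Third, Section 11 speaks of serum concentrations, not troughs, and describing values as observed is a legitimate choice. This stands in part. The endpoint says trough, and excluding post-dose draws only makes sense if troughs are the aim.

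Fourth, the size is modest. With an assumed CV of 40% and the 40 participants per arm of Section 2.5, the standard error of a visit mean is 40%/√40 = 6.3%. The illustrated shift is therefore about 0.3 to 1.8 standard errors. Medians, full listings and counts of doses received are also reported. This stands and supports treating the point as minor.

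A reader might go further and infer that the comparison of 450 with 900 mg, or of UC with CD, is confounded. The SAP does not support that: Section 11 plans descriptive statistics only, with no such comparison, and the modelling has separate plans.

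**Conclusion.** The gap is real but minor. As written, and on the calendar reading of the window, the rule admits samples that are not Q2W troughs into summaries of an endpoint defined as trough concentration. It can also place a loading-dose-only participant in the 450 mg summary.

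The timing result (25 to 31 days since the last dose, against 11 to 17) follows from the SAP's own visit days. The 2 to 11% fall in the mean is only an illustration: half-life and off-schedule share are assumed, and the number of affected samples is unknown. No efficacy or safety analysis in this SAP uses these means.

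Two further inferences are not supported. One is that setting values below the quantification limit to zero makes matters materially worse: no limit is given, and nothing shows that these samples would fall below it. The other is that follow-up samples contaminate the treatment-period summaries: the summaries are already by visit.

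**What to change.** In Section 11:
1. State whether the ±3 day window runs from the nominal visit day or from the last dose.
2. For post-baseline visits through week 14, define an evaluable trough by actual time since the last administered dose: 14 ± 3 days, and pre-dose where a dose is due.
3. Keep all samples in the listing. Flag those not preceded by the scheduled dose or taken after treatment discontinuation, and either exclude them from the by-visit trough statistics or summarise them separately. This also deals with later samples from loading-dose-only participants in the 450 mg arm.

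The cost is a few sentences and one derived variable, time since last dose, from administration dates that should already be collected. The downside is slightly fewer samples per visit, including an occasional on-schedule sample whose interval falls outside 14 ± 3 days.

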12. PHARMACODYNAMIC ANALYSIS

The following pharmacodynamic biomarkers endpoints will be analyzed as part of the statistical analysis:

- Free TL1A change from baseline at each visit
- Total TL1A change from baseline at each visit

Summary statistics for free and total TL1A will be presented by visit. Actual values, change from baseline to each visit will be provided. In addition, graphs of mean change from baseline and mean percent change from baseline to each visit by treatment group will be presented.

The safety analysis set will be used for the pharmacodynamic analyses. Participants with kit mix-ups will be excluded from the analysis.

The analysis will be repeated by response at week 14 as defined by the primary endpoint.

13. PLANNED INTERIM ANALYSIS

Interim analyses for safety (periodic analysis of safety data) are planned for this trial.

The statistical analysis for the IAs will be performed by an external, independent, unblinded analysis team. Release of randomization codes to the unblinded statistician will follow SOP GBP-RD-703. At the IDMC meetings, the unblinded results will be presented and discussed in a closed session of the IDMC.

Unblinded analysis datasets, TLGs, and unblinded analysis outputs will not be disclosed to the sponsor until the trial is completed, database is locked, and randomization codes are released for final analysis. The sponsor will be informed of the IA recommendation; communication format is described in the IDMC charter.

At the safety monitoring meetings, the IDMC will review in detail any safety signal that meets the safety stopping rules described in Section 13.1, and take into account the totality of safety data. The IDMC will make a recommendation if the safety signal and the totality of the safety data warrants stopping the dose/indication/trial.

The IDMC's recommendations to modify an aspect of the trial design should maintain the Sponsor's blind.

For additional details, refer to the IDMC Charter.

13.1. Interim Safety Analyses

Periodic analysis of safety data will be done during the trial.

For each of the 4 types of AEs listed in Table 11, a Bayesian analysis using the Beta-binomial model with a non-informative *Beta* (1, 1) prior will be conducted. The posterior probability of each type of AE will be compared for each dose and the 2 dose levels combined versus placebo. If the posterior probability that the AE rate in the active group is greater than the AE rate in the placebo group reaches a posterior probability cutoff defined below, the stopping rule will be triggered. The analyses and evaluation will be conducted for UC and CD separately and across the entire trial population.

Table 11: Safety Stopping Criteria

AE Type	Posterior Probability Cutoff
Serious adverse events (aggregated)	90%
Grade 3/4 adverse events (aggregated)	90%
Opportunistic and severe and/or serious infections	85%
Anaphylaxis	85%

[figure not shown]
Details on the Beta-binomial model are provided in [Appendix 1](#).

The “basic process” for applying the safety stopping rules is presented in [Figure 1](#).

The safety interim analysis comprises of the following steps:

- Step 1: CD and UC separately, for each type of AE
 - Apply the “basic process” for each indication separately
- Step 2: Combine indications, for each type of AE (not applicable if one indication is stopped)
 - Apply the “basic process” to the combined data from both indications, excluding the dose(s) that were stopped in each indication (if applicable)
- Step 3: Detailed review
 - Review in detail any safety signal that meets the safety stopping rule, taking into account the totality of safety data
- Step 4: IDMC recommendation
 - Make a recommendation if the safety signal warrants stopping the dose/indication/trial

Steps 1 and 2 will be performed periodically by the unblinded analysis group. The Bayesian stopping rules analysis will be performed by the unblinded statistician on a monthly basis, starting after 24 participants are randomized to the trial. Steps 3 and 4 will be performed by the IDMC in case any of the stopping rules is triggered.

Figure 1: Safety Stopping Rules – Basic Process

14. STATISTICAL SOFTWARE

All data listings, summaries, and statistical analyses will be generated using SAS® version 9.4 or later unless noted otherwise.

Graphical presentation of posterior distributions and exploratory predictive modeling for response may be performed using R Version 3.5.2 or above, in the validated Advanced Computational Environment (ACE) (Redhat Enterprise Linux Server version 6.10 or higher).

**15. CHANGES TO ANALYSES SPECIFIED IN THE TRIAL
PROTOCOL**

There are no changes to analyses specified in the trial protocol.

APPENDIX 1. BETA-BINOMIAL MODEL

Bayesian analysis using the Beta-binomial model with a non-informative Beta (1,1) prior will be performed in the following situations:

- Primary analysis (see Section 6.2.2)
- Safety stopping rules at interim safety reviews (see Section 13.1)

Efficacy Analysis – Beta Binomial Model

Using the following notation:

- p = response rate;
- d = active dose group;
- 0 = placebo group;
- i = indication
- Response = clinical remission based on MMS at week 14 for UC; endoscopic response based on SES-CD at week 14 for CD

For each indication (UC or CD) and dose (TEV-48574 450mg Q2W or TEV-48574 900mg Q2W), a Bayesian Beta-binomial model will be fit as follows:

Let n_d^i be the number of participants in the indication in the active dose group

n_0^i be the number of participants in the indication in the placebo group

Let x_d^i be the number of responders in the indication in the active dose group

x_0^i be the number of responders in the indication in the placebo group

Using a non-informative Beta (1,1) prior, the posterior distribution of the response rates in the active dose and placebo groups are given by

$$p_d^i \sim \text{Beta}\left(1 + x_d^i, 1 + (n_d^i - x_d^i)\right)$$

$$p_0^i \sim \text{Beta}\left(1 + x_0^i, 1 + (n_0^i - x_0^i)\right)$$

The posterior probability that the response rate in the active group is higher than the response rate in the placebo group is given by $\text{Prob}(p_d^i > p_0^i)$.

The posterior distribution of the difference between the response rate in the active dose group and the response rate in the placebo group will be estimated by obtaining the empirical difference between 1,000,000 pairs of independent samples drawn randomly from the distributions (p_d^i, p_0^i) .

Let $\{\delta_s^{i,d}\}_{s=1}^{1,000,000}$ be the sampled differences. The probability $\text{Prob}(p_d^i > p_0^i)$ will be estimated by

$$\frac{1}{1,000,000} \sum_{s=1}^{1,000,000} I(\delta_s^{i,d} > 0)$$

Safety Analysis – Beta-Binomial Model

Using the following notation:

- π = AE rate;
- d = active dose group;
- 0 = placebo group;
- i = indication;
- k = AE type

For each of the 4 types of AEs (see Section 13.1, Table 11), dose (single or combined), indication (single or combined) a Bayesian Beta-binomial model will be fitted as follows:

Let n_d^i be the number of participants in the indication in the active dose group

n_0^i be the number of participants in the indication in the placebo group

Let $x_d^{i,k}$ be the number of participants in the indication and active dose group experiencing an AE of the selected type

$x_0^{i,k}$ be the number of participants in the indication in the placebo group experiencing an AE of the selected type

Using a non-informative *Beta* (1,1) prior, the posterior probabilities in the active dose group and placebo group are given by

$$\begin{aligned}\pi_d^{i,k} &\sim \text{Beta}\left(1 + x_d^{i,k}, 1 + (n_d^i - x_d^{i,k})\right) \\ \pi_0^{i,k} &\sim \text{Beta}\left(1 + x_0^{i,k}, 1 + (n_0^i - x_0^{i,k})\right)\end{aligned}$$

The safety stopping rule is given by

$$\text{Prob}(\pi_d^{i,k} > \pi_0^{i,k}) > C^k$$

where C^k is the posterior probability cutoff for the AE type (see Section 13.1, Table 11).

The posterior probability will be estimated as described above for the efficacy analysis.

Numerical examples of the pre-defined safety stopping rules are presented in [Appendix 2](#).

APPENDIX 2. SAFETY STOPPING RULES**Table 12: Safety Stopping Rules – Example 1: Single TEV-48574 dose vs placebo, 18 participants, stopping criterion: 90%**

		Placebo (Number of Participants With Event / Number of Participants)		
		0/9	1/9	2/9
TEV-48574 (Number of Participants With Event / Number of Participants)	0/9	0.500	0.237	0.106
	1/9	0.763	0.500	0.290
	2/9	0.895	0.709	0.500
	3/9	0.956	0.848	0.686
	4/9	0.984	0.929	0.824
	5/9	0.995	0.971	0.915
	6/9	0.998	0.990	0.965
	7/9	1.000	0.997	0.988
	8/9	1.000	0.999	0.997
	9/9	1.000	1.000	1.000

For each combination, the posterior probability that the event rate in the active group is higher than the event rate in the placebo group is presented

Table 13: Safety Stopping Rules – Example 2: Pooled TEV-48574 vs placebo, 36 participants, stopping criterion: 90%

		Placebo (Number of Participants With Event / Number of Participants)		
		0/9	1/9	2/9
TEV-48574 (Number of Participants With Event / Number of Participants)	0/27	0.263	0.064	0.014
	1/27	0.463	0.164	0.048
	2/27	0.611	0.279	0.103
	3/27	0.723	0.396	0.173
	4/27	0.804	0.507	0.257
	5/27	0.863	0.608	0.348
	6/27	0.906	0.694	0.440
	7/27	0.936	0.767	0.531
	8/27	0.958	0.827	0.615
	9/27	0.972	0.873	0.691
	10/27	0.982	0.909	0.759
	11/27	0.989	0.937	0.815
	12/27	0.993	0.957	0.862
	13/27	0.996	0.972	0.900
	14/27	0.998	0.982	0.930
	15/27	0.999	0.989	0.953

For each combination, the posterior probability that the event rate in the active group is higher than the event rate in the placebo group is presented

Table 14: Safety Stopping Rules – Example 3: Pooled TEV-48574 vs placebo, different numbers of participants, stopping criterion: 90%

Total N	Number of Placebo Participants With Event	Number of TEV-48574 Participants With Event	Probability of TEV-48574 >Placebo
36	0/7	8/29	0.912
36	0/9	7/27	0.936
36	1/7	13/29	0.914
36	1/9	10/27	0.909
72	0/16	8/56	0.919
72	0/18	7/54	0.919
72	1/16	13/56	0.916
72	1/18	11/54	0.906

APPENDIX 3. COMPARISON OF PRIMARY ANALYSIS MODEL BETWEEN PROTOCOL AMENDMENT 02 AND PROTOCOL AMENDMENT 04

This section presents a comparison of the major changes in the primary analysis model between Protocol Amendment 02 and Protocol Amendment 04.

The statistical analysis method for the primary analysis was changed from an Emax dose-response- model, which was planned when the study design incorporated 3 treatment arms of TEV-48574 active doses and a placebo arm, to a pairwise comparison approach, primarily due to the removal of 1 active treatment arm. With only 2 active dose arms and a placebo arm, the Emax model would not yield robust or precise estimates for characterizing the dose-response relationship and is no longer appropriate to assess the primary objective of the Phase 2 dose range finding study, which is to characterize the efficacy of 2 doses of TEV-48574 in patients with moderate- to-severe UC or CD.

Additionally, the previous analysis method included a Bayesian borrowing approach that relied on an assumption that both indications, UC and CD, will be concordant (drug is either effective in both indications or not effective in both indications). This is now changed to a simplified Bayesian Beta-Binomial model with no borrowing, and the model is fit separately within each indication, where each dose is compared with placebo. This approach makes minimum assumptions on the dose-response curve shape and the data structure.

Operating characteristics of this approach, for the planned sample size, were considered adequate for a Phase 2 study (See Section 2.5). For UC, for each dose the Type I error rate is 8%, and the probability to declare a dose as successful at the end of the study under the assumption of efficacy is 91%; for CD, for each dose the Type I error rate is approximately 10%, and the probability to declare a dose as successful at the end of the study under the assumption of efficacy is 87%.

Teva had considered other options for the primary analysis model, including a Bayesian hierarchical logistic regression model with dose as a categorical variable. However, similar to the original Bayesian hierarchical model, this model also makes the assumption that the drug was either effective in both indications or not effective in both indications, and it would not yield much gain in efficiency (in terms of the operating characteristics, as noted in simulations) compared with the Beta-Binomial model.

a. Comparison of design, primary analysis model, and futility IA:

Table 15: Comparison of design, primary analysis model, and futility IA between PA02 and PA04

	Old (PA02)	New (PA04)
Design – treatment arms	TEV-48574 1800mg Q2W, 900mg Q2W, 450mg Q2W, placebo	TEV-48574 900mg Q2W, 450mg Q2W, placebo
Model	Bayesian hierarchical Emax dose-response model	Bayesian Beta-Binomial model
Sample size	140 per indication (35 per arm per indication)	120 per indication (40 per arm per indication)
Prior	Non-informative; chosen to encompass the range of plausible values for the model parameters	Non-informative Beta (1,1) prior
Borrowing information across UC and CD	Yes, moderate borrowing	No, the model is fitted separately to each indication
Borrowing information across doses	Yes, dose-response model assumes monotonicity and structure (dose is a numerical variable in the model)	No, the model is fit separately to each dose

